
Placebo Interventions. Pharmaceutical: Placebo pharmaceutical capsules will be prepared by the UF Investigational Drug Service to be visually indistinguishable from the active medication. Placebo administration will be done in the same fashion as was described in the personalized pharmaceutical section to maintain blinding. This includes the same timing for each session and monitoring of cardiovascular responses.

Psychological: The placebo psychological intervention will match the structure and administration of the personalized intervention with the participant remaining blinded to what is received. These components consist of general education and activity principles that did not change psychological measures in our low back clinical trials.^{87, 88} Since these principles are not specific to anatomical region, they are appropriate for use in this study of shoulder pain. The first principle relates to education which will enhance understanding of shoulder anatomy by reviewing: a) structure and arthrokinematics of the shoulder joint; b) muscle anatomy of the shoulder with emphasis on the rotator cuff; and c) potential pain generators in the shoulder. The placebo component is an education approach that accounts for time spent with research staff and dissemination of knowledge relevant to the mechanism of muscle injury, but is devoid of the cognitive restructuring that characterizes the active psychological intervention. ***Thus, this education is not specific to issues that perpetuate pain catastrophizing and can be considered a placebo***. The second principle relates to activity which will be a general exercise program that encourages gradual return of shoulder movement. Briefly, subjects will be instructed in a 24-hour rest period following the injury, then range of motion exercises, and finally muscle

activation will be resumed through isometric exercise. The progression of the exercise will be based on the time from muscle injury, with a progression each day anticipated. ***The placebo component is that it is a generic, protocol based exercise program not specific to activity being avoided due to pain catastrophizing.*** In this manner it accounts for time spent with research staff for general exercise or activity recommendations. The placebo psychological intervention will be scripted and structured so it is provided in a standardized manner for all subjects.

Primary Outcome Measures. The primary outcome measures were selected based on relevance to the clinical model and successful use in the initial funding period. Pain intensity ratings and self-report of upper-extremity disability will be used as primary outcome measures to determine efficacy for shoulder pain duration, peak shoulder pain intensity, and peak upper-extremity disability. ***These constructs have a conceptual link to chronic pain¹ and therefore can be used to characterize the presence of persistent or continued pain following exercise-induced injury.*** The Brief Pain Inventory (BPI) will be used to measure pain intensity as it has been found to have good test-retest reliability over short intervals.⁹⁷ The BPI consists of rating pain intensity on an 11-point numerical rating scale ranging from 0 (no pain) to 10 (worst pain intensity imaginable). The BPI asks subjects to rate current pain and pain at its worst, best and average over the past 24 hours. ***To determine recovery, subjects will complete the BPI daily until they rated their current pain at 0/10 and their worst pain was rated less than 2/10. The number of days it took to reach this recovery criterion will be recorded as duration of shoulder pain.*** The highest worst pain intensity recorded during recovery will be recorded as the peak shoulder pain intensity. The Disabilities of the Arm, Shoulder, and Hand Questionnaire (DASH) will be used to assess upper-extremity disability and we will continue to use a validated abridged version of the DASH (the QuickDASH) which consists of 11 functional items, with total scores ranging from 0 (not disability) to 100 (complete disability).⁹⁸ We will use the QuickDASH because shoulder pain can also affect distal function of the arm and hand, and we wanted to obtain a global upper-extremity assessment. Similar to the BPI ratings, QuickDASH scores will be recorded daily until recovery and the highest score during this period will be recorded as peak upper extremity disability. Another advantage of these measures is they are widely accepted as primary outcome measures in clinical studies, and were used as such in the initial funding period. Therefore, these measures will allow for specific effect size estimates for a subsequent randomized clinical trial in post-operative shoulder pain.

Secondary Outcome Measures. These measures represent underlying mechanisms that we hypothesize to be related to how the personalized interventions affect pain relief. These measures will be obtained at the same time each day (relative to the time of the initial shoulder injury) to avoid unwarranted variation.

Molecular: These measures will capture relevant inflammatory biomarkers. The low COMT activity of our high-risk group results in increased catecholamine activity, which augments release of proinflammatory cytokines under conditions of stress.⁹⁹⁻¹⁰¹ This catecholamine-evoked cytokine release can be attenuated by propranolol.⁹⁹⁻¹⁰² Moreover, catastrophizing, which also characterizes our high-risk group, has been associated with greater increases in circulating proinflammatory cytokines following both acute pain¹⁰³ and induction of pain-related negative emotions.¹⁰⁴ Thus, we hypothesize that personalized pharmaceutical or psychological intervention will significantly attenuate cytokine levels, with the greatest reduction observed in the combined personalized intervention condition. Moreover, because the increased pain evoked by COMT inhibition has been found to be mediated by increased circulating cytokines and reversed by blockade of beta-adrenergic (β 2 and β 3) receptors,⁷ we further expect that the attenuation of cytokine release will be associated with the efficacy of our combined personalized intervention for reducing pain and disability. Thus, we plan to perform assays for several inflammatory cytokines, including IL1B, IL6, IL8, and TNF α at baseline, immediately after the exercise-induced injury, and at regular intervals (Figure 5). All assays will be performed by the Metabolism and Translational Science Core of the Claude D. Pepper Older Americans Independence Center using commercially available kits with which they have extensive experience.

Psychological: In addition to the aforementioned PCS, the Tampa Scale of Kinesiophobia which is an 11-item (TSK-11), 4 point rating scale to quantify avoidance and re-injury beliefs^{105, 106} and the Fear of Pain Questionnaire (FPQ-III) which is a 30-item, 5-point rating scale to quantify fear about specific situations that normally produce pain¹⁰⁷⁻¹⁰⁹ will be used to capture psychological processes. Consistent with a fear-avoidance model of musculoskeletal pain,¹¹⁰ we hypothesize that the personalized psychological intervention will reduce these levels significantly via cognitive restructuring providing subsequent decreases in disability and pain.

Pain Sensitivity Regulation: These measures characterize nervous system processing of standard stimuli so that central or peripheral sensitization states indicative of pain amplification can be detected.^{41, 43, 111} Pain amplification is important to account for separately because it is hypothesized as a precursor to chronic musculoskeletal pain conditions that can occur with or independent of the molecular and psychological measures.²⁸ The potential contributors to pain amplification are multifactorial, therefore we hypothesize that the combined personalized intervention group will show the largest reduction in measures indicative of pain amplification. All pain sensitivity measures will be obtained by psychophysical sensory testing as per established protocols established from the initial funding period.^{45-47, 111} All stimuli will be delivered to bilateral upper extremities to allow for side to side comparisons. Stimulation sites will be varied to prevent carryover effects due to local sensitization. The stimuli are to be applied by a research assistant blinded to intervention status who ensures proper application and the range of stimulus intensities to be used (30-54°C) will be presented beforehand to each subject. All subjects will undergo a brief training with the stimuli to be tested. We have found this procedure to be useful because it familiarizes subjects with the stimulus range, tends to obviate range effects in psychophysical scaling, and helps alleviate subject anxiety about the upper limit of stimulus intensities to be used. The research assistant will record patient visual analogue scale (VAS) response to each stimulus used. The VAS will consist of a 10 cm line whose endpoints are designated as 'no pain sensation' and 'the most intense pain sensation imaginable'. In order to standardize the scaling instructions, standard instructions¹¹² will be used for all subjects. The specific pain sensitivity regulation measures to be collected include suprathreshold heat pain responses, pressure pain threshold, and conditioned pain modulation. Exact parameters for these measures are explained in more detail in publications from the initial funding period.^{45-47, 111} These measures were selected because we expected them to be responsive to the combined personalized intervention and associated with pain relief. For example, elevated suprathreshold heat pain responses normalized post-operatively in the clinical cohort⁴⁶ and its changes were associated with improvements in post-operative shoulder pain and disability.¹¹³

C4. Statistical Analysis Plan

All statistical analyses will be performed using the SAS software, version 9 (SAS Institute Inc, 1996). Summary statistics will be provided for baseline measures by intervention groups to determine if randomization produced balanced groups. Any group imbalance will be investigated further to determine if covariates should be considered. For Specific Aim #1, our primary analysis for efficacy will compare shoulder pain duration (i.e. *number of days until subject rated their current pain at 0/10 and their worst pain was rated less than 2/10*) across the four randomly assigned groups with the use of logistic regression. Consistent with the initial funding period, the primary outcome variable will be dichotomized based on duration of at least 7 days or not. There is an *a priori* plan to include age, sex, and race as covariates in this analysis, additional variables will be added as covariates only if imbalanced across groups and correlated with outcome measures. We anticipate very little missing data because this is a pre-clinical study, but any missing outcomes will be predicted by subject pain intensity trajectory plus baseline demographic factors. The primary comparison between the combined personalized intervention and the combined placebo condition will be tested at the 0.05 significance level, while the other five between group contrasts will be tested using a step-down procedure. For the other primary outcomes (peak pain intensity and upper-extremity disability as continuous measures) we will perform a similar analysis process (i.e. same considerations for post randomization imbalance, covariates, and missing data) with linear regression analysis to compare the four intervention groups. For Specific Aim #2, we will fit path models with predetermined orders to investigate the direct (intervention group) and indirect effects (through the mediating psychological, molecular, and pain sensitivity paths) of the randomly assigned condition on pain relief. The combined placebo intervention will serve as reference group for these analyses. The total, direct and indirect mechanistic effects on pain duration (dichotomous) and peak pain intensity and upper-extremity disability (continuous) will be estimated and tested at the 0.05 significance level for the comparison of assigned conditions. Specifically, the total effect will be estimated and tested through a logistic regression for pain duration and a general linear model for peak pain intensity, both of which include the assigned intervention conditions as independent variables while controlling for participant age, sex, and race. The direct effect will be estimated and tested with the use of the same models including the same independent variables, but controlling for mediating molecular, psychological, and pain sensitivity variables in addition to age, sex and race. The two regression models in the second step will reveal the contributions of the mediating psychological, molecular, and pain sensitivity variables on pain relief. On the other hand, the indirect effect will be calculated based on the difference between the total and direct effects. In addition, we will conduct a third

set of regression analyses to evaluate the effect of the assigned condition on the mediating variables which will determine which indirect paths are statistically significant.

C4. Sample Size Estimate and Study Timeline

A total of 448 high-risk subjects will be recruited. In the initial funding period we found that 40.5% of high risk subjects had pain duration \geq 7 days while 21.4% of the low risk group had long duration (Table 1). In our power analysis, we assumed that 40% of the combined placebo group will have long pain duration (rate for high risk subgroup), while the rate for the combined personalized intervention group will be 20% (rate for low risk group). Those with one personalized intervention were assumed to have 30% chance of having duration \geq 7 days. The planned sample size will enable us to have 80% power to detect the assumed differences across the four intervention groups and 91% power for the primary comparison between the combined personalized and the combined placebo interventions at a type-I error level of 0.05. The overall BISP timeline is in Table 3.

Table 3. Timeline and Key Periodic Events for BISP

Year 1		Year 2		Year 3		Year 4		Year 5					
Start Up	Quarterly Meetings with Research Team Annual Progress Reports to Institutional Review Board, Data Safety Monitoring Body, and NIH												
	Screening, Recruitment (annual rate = 96-120 participants), Intervention, and Follow Up												
	Scientific Conference		Scientific Conference		Scientific Conference		Scientific Conference		Scientific Conference				
On Site Consult		On Site Consult		On Site Consult		On Site Consult		On Site Consult	Analysis, Dissemination				

C5. Potential Pitfalls and Alternative Approaches

1) *Feasibility of Proposed Sample Size.* In the initial funding period we recruited 340 subjects. There is potential for higher recruitment rate in this proposal because it involves only the exercise-induced injury cohort of healthy volunteers. Recruiting for the clinical cohort was much more time intensive. Drs. [name] and [name] have experience in large scale recruitment from OPPERA⁵⁴ and our planned screenings will generate sufficient high-risk participants. The protocol requires at least five days of participation from participants and we had an outstanding completion rate (189/190) during the initial funding period. Therefore, retention and missing data are not expected to be a concern. If there is more missing data than anticipated we will account for it in our statistical analysis. 2) *Lack of Shoulder Specific Intervention Pilot Data.* Pilot data demonstrating effect sizes will be vital when proposing a clinical trial in the post-operative setting. This renewal proposal includes established pharmaceutical⁸ and psychological⁸⁶ interventions that have demonstrated effects in clinical populations (orofacial and low back pain respectively) from studies conducted by members of this research team. We will monitor intervention responses for expected results on process variables and adjust the intervention components if indicated. 3) *Low Risk Subgroup.* Intervention effects for low risk subjects will be unknown, and these effects potentially have scientific interest. However the pragmatic advantages of greater research design efficiency and direct relevance to clinical investigations justified focus on the high risk subgroup. 4) *Exploratory Analyses.* We intentionally presented a focused statistical analysis plan to determine the efficacy (Aim #1) and mechanisms (Aim #2) of the personalized interventions described in this proposal. We do acknowledge that response to these interventions may not be as predictable as we have hypothesized. In the unlikely event that the Aim #1 analyses indicate no group differences we will perform additional analyses to inform future research in this area. For example as already mentioned, there is potential for sex differences in pain sensitivity⁵⁸⁻⁶⁰ and COMT variant influence on pain sensitivity⁶¹ to impact study results. We have accounted for this with stratified randomization based on sex and by *a priori* including sex as a covariate in primary analyses. In the case of null findings, however, a specific exploratory analysis will determine if sex-specific intervention effects occurred. For Aim #2 other analyses will be more exploratory in nature (e.g. post-hoc treatment responder) and will be enhanced by the storage of excess DNA, plasma, and RNA so additional genetic predictors and molecular mechanisms can be considered (assuming subjects consent for that use).

C6. Summary and Future Research Directions

Chronic musculoskeletal pain is a significant public health problem. Since 2006 this talented, multidisciplinary team has been working to develop personalized musculoskeletal pain management options. Renewal of this application will allow the important predictive work from the initial funding period to be transitioned to a high impact pre-clinical intervention study. Ultimately, we hope that completion of the proposed study provides foundational data to substantially improve standard of care by identifying personalized interventions that offer pain relief for those most at risk for developing chronic shoulder pain.

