This renewal application extends and translates this work by determining efficacy and mechanisms of personalized interventions targeting the genetic and psychological factors that make up the high-risk subgroup. We will use a validated pre-clinical model in the renewal application because it controls the injury mechanism and allows for high treatment fidelity. The pre-clinical model also allows us to determine how underlying changes in molecular processes, psychological factors, and pain sensitivity regulation are associated with pain relief. Furthermore this pre-clinical model has an established link to a post-operative clinical model. **In the renewal application we propose a study that will provide proof of principle that personalized pain interventions favorably alter outcomes and mechanisms for individuals that, without the personalized intervention, would go on to develop chronic shoulder pain.**

B. Innovation

Several aspects of the Biopsychosocial Influence on Shoulder Pain (BISP) design are innovative. BISP follows the structure described by [name] et al^{28, 37} for investigating risk factors contributing to the development of chronic musculoskeletal pain conditions. Figure 1 graphically depicts the BISP conceptual model, which focuses on genetic and psychological factors as contributing to pain outcomes in parallel pre-clinical and clinical cohorts. From the outset, genetic and psychological factors were *a priori* selected based on their potential to be targets of personalized interventions in future studies. Thus, the original intent of BISP was to transition from predictive to intervention phases, pending direction provided by data generated in the initial funding period. Additional innovative aspects of BISP are highlighted below.

[figure not shown]

Figure 1. Biopsychosocial Influence on Shoulder Pain Conceptual Model
 BISP included: 1) *a priori* determined genetic and psychological risk factors for experimental pain sensitivity and clinical outcomes and 2) parallel investigation in pre-clinical and clinical cohorts. Dark lines represent the hypothesized pathways that the genetic and psychological factors influence. Dotted lines represent direct pathways that were tested as competing hypotheses. The shaded bi-directional line indicates that minimal associations between genetic and psychological factors were observed.

provides confidence that additional findings from our pre-clinical model will continue to have clinical relevance.

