
Randomization. There are reported sex differences in pain conditions,^{58, 59} and we have observed that females report higher pain sensitivity in our studies of shoulder pain.⁶⁰ Sex differences in how *COMT* impacts pain sensitivity has also been described, with females having a stronger association with pain sensitivity for certain genetic variants.⁶¹ Therefore randomization will be balanced to ensure equal allocation for males and females in the different intervention groups (i.e. sex stratified). The randomization scheme will be prepared by computer and completed prior to the start of the study. After the randomization list is generated treatment assignments will be contained in sealed, numbered envelopes. Envelopes will be opened in sequential order as each participant enters the study by research staff blinded to application of interventions (i.e. treatment assignment and allocation will be by different research personnel). We will randomize prior to muscle injury to ensure propranolol is absorbed by the system before muscle injury. Propranolol administration before injury allows for any immediate pre-emptive effects on the molecular or pain sensitivity regulation measures to be detected during the baseline session (Figure 5). This administration also matches when propranolol would be administered in a clinical model (i.e. pre-operatively) so that translational component will be maintained.

Exercise-Induced Shoulder Injury. Research personnel performing the muscle injury protocol will be blinded to randomization results. Subjects will undergo exercise-induced shoulder injury to the dominant arm. The

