specific eccentric exercise fatigue protocol uses isokinetic equipment⁶²⁻⁶⁶ and is an established protocol from the initial funding period^{16, 19, 40} and other prior published studies.^{18, 67} The fatigue protocol will be performed prior to randomization to maintain blinding to prevent bias. Briefly, shoulder fatigue will be induced using a Kin-Com (Chattanooga, TN) isokinetic dynamometer. Subjects will be placed in a seated position, with shoulder straps applied to support the torso. Then, the dominant shoulder will be placed in the scapular plane because this position has been associated with high test-retest reliability and has decreased impingement of the greater tuberosity under the acromion.^{62, 68} Maximum voluntary isometric contraction (MVIC) will be determined by having the subjects perform 5 repetitions of isometric shoulder external rotation. Subjects will be asked to perform the contractions with maximal effort and given verbal encouragement during the contractions. The MVIC will be determined by averaging peak force from the middle 3 repetitions.^{69, 70}

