After MVIC is determined, subjects will complete eccentric/concentric external rotation repetitions to induce muscle fatigue and microtrauma. The first set of repetitions will be completed at 100 degrees/second to familiarize the subjects with the testing apparatus. Then, the speed will be lowered to 60 degrees/second for 3 sets of 10 repetitions that constituted the fatigue protocol. After completing those repetitions, subjects will be re-tested to determine if they can generate more than 50% of their respective MVIC. Previous research has indicated the inability to achieve 50% of initial peak MVIC is an indicator of muscle fatigue.⁶³⁻⁶⁶ If they are unable to achieve at least 50% of their MVIC, the fatigue protocol is terminated. If they are able to generate more than 50% of their MVIC, subjects will perform additional sets of 10 repetitions at speeds of 45 degrees/second. This will be repeated until their peak force is less than 50% of the initial MVIC. Subjects will be allowed to rest 30 seconds between sets and the total amount of work performed to reach muscle fatigue will be recorded. The goal of the injury protocol is to induce delayed onset muscle soreness (DOMS) in the rotator cuff musculature. Shoulder DOMS is a clinically relevant model because subjects experience increased pain intensity, loss of range of motion, inflammatory responses, altered proprioception, and the use of self-care behaviors.^{63, 64, 66, 71-75} Additional relevance of this model for post-operative shoulder pain was confirmed in the aforementioned studies from our initial funding period.

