The UF Investigational Drug Service will prepare long-acting propranolol (Propranolol LA) 60 mg to be administered orally in the Pain Clinical Research Unit once daily for the five days of the protocol. This dose will provide a bioequivalent dose to that recently reported in a clinical study examining responses to propranolol among patients with TMD pain.⁸ The first dose will be administered prior to the exercise-induced shoulder injury to mimic pre-operative settings and to allow for immediate effects to be observed during the baseline session. Subsequent doses will be applied at the beginning of each session. Cardiovascular response (i.e. ECG, HR and BP) will be monitored 60 minutes after drug administration by a research nurse. The purpose of

this monitoring is for safety (early identification of potential adverse events) and efficacy (demonstrate medication absorbed). These measures will be recorded by the research nurse in a blinded manner, and not made available to any other research personnel performing testing within that session, unless subject safety is a concern. These data will be used by the investigator team as a manipulation check to assure that propranolol absorption is occurring, and allow for adjustments to be made early in the protocol if not.

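### Total work in the fatigue protocol varies between participants and is recorded but never analysed, and the documents disagree on whether the first capsule comes before or after it

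*Combined protocol and SAP*

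**What the plan says.** **Stopping rule (C3, Exercise-Induced Shoulder Injury).** Maximum voluntary isometric contraction (MVIC) is measured first. Everyone then completes a familiarization set and three sets of 10 repetitions at 60 degrees/second. Participants who can still exceed half of their own MVIC go on with sets of 10 at 45 degrees/second: "This will be repeated until their peak force is less than 50% of the initial MVIC". No fixed workload or maximum number of sets is given. The same section says that "the total amount of work performed to reach muscle fatigue will be recorded".

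**Order of capsule and injury.** Three statements bear on this, and they do not agree:
- C3, Randomization: "We will randomize prior to muscle injury to ensure propranolol is absorbed by the system before muscle injury".
- C3, Personalized Interventions: "The first dose will be administered prior to the exercise-induced shoulder injury to mimic pre-operative settings".
- C3, Exercise-Induced Shoulder Injury: "The fatigue protocol will be performed prior to randomization to maintain blinding to prevent bias".

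**Analysis (C4, Statistical Analysis Plan).** For Aim 1 there is a "plan to include age, sex, and race as covariates in this analysis", and "additional variables will be added as covariates only if imbalanced across groups and correlated with outcome measures". The balance check that feeds this rule covers baseline measures. The Aim 2 mediators are molecular, psychological and pain-sensitivity variables. Total work is not named in any model, table or outcome.

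**Reason for the model (A3).** It was chosen "because it controls the injury mechanism and allows for high treatment fidelity".

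**The concern.** The variable part of the injury ends when the participant fatigues, so the amount of work done is a result of the session. If the capsule is given first, MVIC (the denominator of the stopping rule), the number of extra sets and total work are all post-dose quantities. Should propranolol change maximal force or time to fatigue, the propranolol and placebo-capsule arms would receive different amounts of injury.

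The plan obtains the indirect effect as the total effect minus the direct effect, with only the three named families of mediators. A drug effect running through work would then appear in one of two wrong places. It could fall into the direct effect. Or it could pass through the cytokines, which are measured immediately after the injury, and be read as the hypothesised beta-blockade mechanism.

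This matters for what the trial is meant to support. The stated purpose is to identify mechanisms of pain relief and carry them to pre-operative dosing. A surgical injury is not ended by the patient's muscle fatigue, so a benefit that came from a smaller exercise injury would not be expected to carry over. The planned analyses do not look at this, although the main variable needed is collected.

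**Working it through.** **Step 1. The plan's own power figure.** Inputs from C4, Sample Size Estimate: 448 participants, rates of 40% and 20%, alpha 0.05. Assumed: equal allocation (448/4 = 112 per group) and a two-sided test. With pooled variance under the null:
- mean rate = 0.30; SE0 = √(2 × 0.30 × 0.70 / 112) = 0.0612
- SE1 = √((0.40 × 0.60 + 0.20 × 0.80) / 112) = 0.0598
- power = Φ((0.20 − 1.96 × 0.0612) / 0.0598) = Φ(1.34) = 91%

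This matches the stated 91%. The four-group figure also reproduces: 79.0% by Pearson and 79.7% by likelihood ratio, on 3 degrees of freedom, against a stated 80%. Nothing in this point disputes either figure.

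**Step 2. What total work is under each order.**

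| Order | Can the assigned capsule affect MVIC, sets or work? | Status of total work |
|---|---|---|
| Capsule before injury (Randomization; Personalized Interventions) | Possible | Post-dose, possible mediator |
| Injury before randomization (Exercise-Induced Shoulder Injury) | No | Baseline covariate |

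The plan gives total work no role in either case.

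**Step 3. How large could a path through work be?** The documents give no effect of propranolol on work and no relation of work to pain duration, so every input here except the 40% rate is an assumption. Model: logit P(duration ≥ 7 days) = a + ln(OR) × W, where W is total work in SD units, normal with mean 0 and SD 1 under placebo capsule. The intercept a is set so that the marginal rate is 40%. The mean of W is then shifted, with no other drug effect.

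| OR per SD of work | Shift in mean work (SD) | Rate of ≥ 7 days | Change from 40% |
|---|---|---|---|
| any | 0 | 40.0% | 0 |
| 1.1 | −0.10 | 39.8% | −0.2 |
| 1.2 | −0.25 | 38.9% | −1.1 |
| 1.5 | −0.25 | 37.7% | −2.3 |
| 1.5 | −0.50 | 35.4% | −4.6 |
| 2.0 | −0.25 | 36.3% | −3.7 |
| 2.0 | −0.50 | 32.7% | −7.3 |
| 1.5 | +0.25 | 42.4% | +2.4 |
| 2.0 | +0.50 | 47.7% | +7.7 |

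The illustrative range is therefore about −7 to +8 points. For scale, the sample size section assumes 10 points (40% to 30%) for one active component. The range shows what the inputs imply; it is not an estimate.

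**Step 4. Would a by-arm comparison be informative?** Under equal allocation there are 2 × 112 = 224 participants per capsule type. The difference in mean work detectable with 80% power at two-sided 0.05 is (1.960 + 0.842) × √(2/224) = 0.26 SD. The check would therefore detect shifts near the upper end of the assumed range, but could miss those below about a quarter of an SD.

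**The case against.** **The premise is disputed inside the protocol.** If the fatigue protocol precedes randomization, no assigned capsule can affect it. This stands, and it is why the order must be settled first. It does not remove the point: under that order total work is a pre-randomization variable that the plan still does not name.

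**The mechanism is undocumented.** No passage says that propranolol changes force, fatigue or work, or that work predicts duration. This stands. A reader might infer that propranolol makes the injury smaller and that several points of any observed benefit would be an artefact. The documents do not support that: they give neither direction nor size, and the same model yields a negligible change or a rise in the rate under other inputs.

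**The injury is partly standardized.** Four sets are common to all, and the stop is relative to each person's own MVIC, which aims at a common degree of fatigue. A3 claims control of the injury mechanism, not a fixed workload, so there is no contradiction with that claim. This stands, but a common degree of fatigue does not imply equal work.

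**Other data bear on the question.** The plan looks for immediate drug effects in the baseline session and measures cytokines before and just after injury. This is useful, but it does not tell whether the arms did the same work.

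**The covariate rule might bring work in.** It is generic and tied to a baseline check. If it did admit post-dose work, it would put a possible mediator into the primary model.

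**Total work is an imperfect measure of injury.** It also reflects strength and effort, so an estimate holding it fixed needs assumptions. This stands and limits what that estimate can be used for.

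**Conclusion.** The point holds as a gap in the plan for interpretation. Total work varies, is recorded and has no analytic role, and the passages that determine its role contradict each other.

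Under the drug-first order, the Aim 2 models cannot distinguish a propranolol effect on pain processing from one on the amount of injury. Whether such an effect exists is unknown. The illustrative shift of about −7 to +8 points in the 40% rate includes zero and rests entirely on the assumed odds ratios and shifts in work.

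A reader might also infer that the primary test is biased or its error rate inflated. It is not: the randomized Aim 1 comparison remains a valid test of the total effect of assignment, and no sample size or power figure changes. What is affected is the mechanism conclusion, and its translation to surgery, in the arms that receive propranolol. The improvement is cheap and worth making.

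**What to change.** 1. **Reconcile the order** of randomization, first capsule and fatigue protocol across the three C3 sections. The role of total work follows from it.
2. **If the capsule comes first**, prespecify:
   - a comparison of total work, number of sets and initial MVIC between the propranolol and placebo-capsule arms;
   - total work as an added path in the Aim 2 models;
   - that the pain-modulation and surgical-translation claim for propranolol will be qualified if the arms differ;
   - that post-dose work may not enter the primary model through the imbalance rule.

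   Any estimate holding work fixed should be supportive only. It should be labelled as conditioning on a post-dose variable and as assuming no unmeasured common causes of work and pain.
3. **If the injury precedes randomization**, prespecify total work as a baseline covariate.

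Under the drug-first order the primary model stays as written. The cost is some SAP wording and a few models on data that the protocol already generates, with no extra participants. The downside is a supportive estimate that rests on assumptions the trial cannot verify.
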